### Aim 2: Pilot RCT

Pilot RCT sample size calculation using a confidence interval approach: To obtain a precision interval with a standardized half-width of 0.50 (akin to a medium effect) with 90% assurance, we have planned a sample size of 60 ( $n_{Trt}=40$ ,  $n_{Con}=20$ ), assuming  $\geq 85\%$  retention at 16 weeks. This provides reliable estimates of between-treatment differences in change in amygdala activation for nonconscious threat-related reactivity and change in DLPFC activation for cognitive control from week 0 to 16 in Criterion 1. In Criterion 2, a sample size of 60 will also be sufficient to detect a correlation coefficient of  $r=0.4$  with 0.80 power and 2-sided  $\alpha=0.05$ . We are not focused on smaller correlations ( $r<0.4$ ) because their implications are likely to have more limited clinical relevance.

The criteria to evaluate neural target engagement are as follows:

**Criterion 1.** The level of task-evoked activation for either the amygdala for nonconscious threat-related emotional reactivity or for the DLPFC for cognitive control improves meaningfully from week 0 to 16 in the Lumen group compared with the waitlist control group.

Criterion 1 is tested via  $t$  test that compares the change from week 0 to 16 in the Lumen group with that change in the waitlist control group. Participants are analyzed based on the group to which they are assigned using all available data. The  $t$  test described above can be readily expanded for exploratory subgroup analyses by applying to each subgroup (e.g., female vs. male).

**Criterion 2.** Change in the level of task-evoked activation of a neural target that meets Criterion 1 correlates with temporally concurrent change from week 0 to 16 in self-reported measures within the corresponding PST theory-based construct for emotional reactivity or cognitive control. We consider correlations of  $r\geq 0.4$  meaningful.

To test Criterion 2, we examine the regression change of the amygdala activity from week 0 to 16 on change in self-reported measures of emotional reactivity (worry, affect) from week 0 to 16, controlling for baseline values of the self-reported measures and group assignment. We expect that the coefficient for the change in amygdala activation is significant and positive in the direction of improvement in its

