The SPEAC project is at the frontier of research on developing a voice-based AI agent (Lumen) for PST and validating its effect on *a priori* neural targets, and the Pilot RCT (Study 1) is to estimate possible effects of target engagement, which, if promising, will support further investigation to confirm target engagement in Study 2. In this context, we apply a precision interval approach (see Section A above) to determine Criterion 1. We define that, compared with the waitlist control group, the Lumen PST treatment group will demonstrate a *meaningful improvement* in a neural target if the standardized between-group mean difference is at least Cohen's  $d=0.3$  in favor of Lumen (small effect; 50% of that in ENGAGE). At this effect size, the upper limit of the precision interval overlaps with  $d=0.8$  (large effect) given a standardized half-width of 0.5 with 90% assurance that the interval contains the true mean difference based on the power analysis. We consider such a finding to be meaningful and will suffice Criterion 1.

- ii. Criterion 2. Change in the level of task-evoked activation of a neural target that meets Criterion 1 correlates with temporally concurrent change from week 0 to 16 in self-reported measures within the corresponding PST theory-based construct for emotional reactivity or cognitive control. As noted, we consider correlations of  $r=0.4$  or greater meaningful. Specifically:
  - a. If the amygdala target exhibits a meaningful improvement in the Lumen group vs. the waitlist control (Criterion 1), then we will examine whether that improvement is significantly correlated with improvements in validated self-report measures of emotional reactivity (worry, affect) over the same 0-to-16-week interval.
  - b. If the DLPFC target exhibits a meaningful improvement in the Lumen group vs. the waitlist control (Criterion 1), then we will examine whether that improvement is significantly correlated with improvements in cognitive control (problem solving, dysfunctional attitudes) over the same 0-to-16-week interval.

Criterion 1 is tested via *t* test that compares the change from week 0 to 16 in the Lumen group with that change in the waitlist control group. Participants are analyzed based on the group to which they are assigned using all available data. The *t* test described above can be readily expanded for exploratory subgroup analyses by applying to each subgroup (e.g., female vs. male).

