### **B.2. Treatment effects on PROs and ecological measures**

Secondary analyses will compare differences in discrete changes in PROs from week 0 to 16 and trajectories of change based on intensive time-series ecological measures between the Lumen and waitlist control groups. Analyses of the treatment effects on PROs will employ the same *t* test approach as described above for testing Criterion 1 for target engagement.

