Longitudinal mixed modeling will be applied to analyses of the ecological measures (mood, stress, appraisal, and coping) where the design is  $\text{Group} \times \text{Time} = 2 \times 8$  as these measures will be obtained (using a validated measurement burst design) daily for 7 days every 2 weeks (on weeks 0, 2, 4, 6, 8, 10, 12, 16). During active treatment in the Lumen group, this will occur for 3 days prior to, the day of, and 3 days after each scheduled PST session. For waitlist controls, this will occur for 7 days starting on Sunday of each assigned week. This allows us rich and detailed information on ambulatory changes over the course of treatment, as well as estimates of proximal responses to treatment within 3 days immediately post a PST session. For example, using the means of ecological measures over the 3 pre-PST days (to avoid confounding estimates with proximal treatment response) in the Lumen group and the first 3 days in the waitlist control group every 2 weeks as DVs, we will characterize their trajectory of change in terms of orthogonal linear, quadratic, and cubic components. We also will examine regression spline versions of these trajectories for visualization and interpretation. In a more exploratory vein, for each set of 7 daily ecological measures, collected biweekly, we will use piecewise linear models to characterize proximal responses to treatment based on the change of the 3 post-treatment days' means from the 3 pre-treatment days' means (omitting treatment day 4) in the Lumen group and the corresponding biweekly change of the last 3 days' means from the first 3 days' means (omitting day 4) in the waitlist control group. As these differences are nested within the 8 biweekly measurement bursts, and thus can be examined longitudinally, we can consider whether there is change over weeks in patients' proximal responses to each PST session (in terms of the ecological measures). In all analyses, all available data for each DV will be used and missing data will be handled directly through maximum-likelihood estimation via mixed modeling, supplemented with imputation and sensitivity analysis (see Handling Missing Data in Section B.4 below).

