#### **B.4. Intention to Treat (ITT) and Handling Missing Data**

Clinical trials such as the one proposed must face the issues of dropout and missing data. We have put in place a strong plan to ensure maximum retention of participants through the course of the study, with a projected 85% or greater retention (see the *Recruitment and Retention Plan*). Data missing completely at random (MCAR) may be analyzed “as is” without imputation, as it does not introduce bias into estimates and inferences. More commonly, data are missing at random (MAR) owing to covariate-dependent events (e.g., irregular work shifts, children’s illness, transportation, and scheduling foul-ups). Our primary analysis technique, linear mixed models, is robust for MAR and provides unbiased estimates of model parameters without imputation. (One may impute as well, but the benefit is usually modestly improved power rather than changes to conclusions.) The more serious concern for behavioral interventions is the possibility that data will be missing not at random (MNAR). This occurs when dropout or missingness is related to the level of the outcome of interest (e.g., a participant’s level of depression or anxiety). If treatment is working well and symptoms of depression and anxiety have lessened, then participants may feel continuation in treatment is not necessary or beneficial. They drop out or miss sessions because the treatment seems to have worked. On the other hand, if participants experience no improvement in symptoms, they may drop out or miss sessions because they are discouraged that the treatment seems not to have worked. In either case, the loss of data is related to the outcomes under study and has the potential to bias the study’s conclusion about the intervention. Handling the problem of MNAR is difficult. First, there is no test for the presence of MNAR (*vs.* MAR). Second, there are many possible underlying sources of MNAR and there is no guarantee that explorations of missing data patterns will clearly reveal those sources. Third, missing data imputation for MNAR necessarily makes strong and untestable statistical assumptions, so that conclusions from imputed MNAR datasets must remain tentative. This picture reinforces our strong commitment to participant retention (see the Study 1 *Recruitment and Retention Plan*).

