Missing data imputation implemented via SAS procedures MI, MIANALYZE, and MCMC will be carried out to reexamine all primary and secondary analysis. This effectively implements ITT as traditionally conducted. Specifically, both missing outcomes and covariates will be imputed under the

assumption that data are MAR. The fully conditional specification (FCS) approach allows each variable type to be imputed with an appropriate model: linear, discriminant, logistic, or Poisson regression. The algorithm for FCS is implemented in procedure MI: 100 imputed data sets will be created, each imputation is analyzed using MIXED, and finally MIANALYZE combines 100 sets into final estimates. This approach to MAR has been widely adopted given its robust performance. Because linear mixed models estimated via direct likelihood as in MIXED offer unbiased estimates under MAR, the benefit of multiple imputation lies in compliance with the ITT fill-in requirement and modestly increased power. We anticipate these results to differ little from those provided by the primary analysis.

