#### ***B.4.a. Sensitivity of results to missing data assumptions***

These will be conducted by varying the models used for imputation. There is no test for NMAR, but we will examine missing data frequency by condition and in covariate subgroups to detect and diagnose differential dropout. If warranted, we can shift to a Bayesian joint modeling approach to imputation using MCMC. The mathematical statistical underpinnings of sensitivity analysis for missing data imputation have advanced substantially (see, for example, the treatment of selection models in Chapter 8 of Daniels and Hogan). However, the software implementation of these techniques has lagged behind the theory. Simpler approaches have been implemented in SAS at this time; however, the more complex techniques involving semiparametric specification of the Daniels and Hogan extrapolation model are not readily available. During the data collection years, this problem will likely be resolved. Here, we mention 3 approaches that seem feasible now: (1) With just a few data collection waves, the number of frequently occurring missing data patterns is likely 3 to 6 for neural targets and PROs and 8 to 10 for ecological assessments and treatment progress measures (some infrequent patterns can be grouped together); these patterns can be used to specify a pattern mixture model for the missing data. Such models merely include an indicator variable for each pattern and thereby provide a straightforward means to adjust results for missing data. If results are not much altered by inclusion of pattern indicators, then concern about missing data assumptions is diminished; (2) Mallinckrodt et al. reviewed simulation and other studies of the impact of MNAR on trial results (primary analyses like those we plan) and concluded that the impact of violations is rarely substantial. The R statistical environments add-on package ‘mice’ now has capabilities to create particular violations of MAR and MNAR assumptions, so that simulation-based exploration of violations using our own data will now be possible; and (3) SAS PROC MI has now incorporated an option to use a SCALE parameter (suggested range between 1.5 and 2.0) to explore the sensitivity of results to imputations relying on the MAR assumptions.

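### The missing-data section relies on mixed models, but Criterion 1 and the PROs use a t test on change; and for outcomes seen only at weeks 0 and 16, the pattern-indicator check cannot give the reassurance claimed for it.

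*Combined protocol and SAP*

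**What the plan says.** Appendix 3, B.4 states: "Our primary analysis technique, linear mixed models, is robust for MAR and provides unbiased estimates of model parameters without imputation". It then plans multiple imputation under MAR as a re-examination of all primary and secondary analyses, in which "each imputation is analyzed using MIXED", and adds: "We anticipate these results to differ little from those provided by the primary analysis".

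B.1 decides Criterion 1 by a t "test that compares the change from week 0 to 16 in the Lumen group with that change in the waitlist control group". Section 9.0 repeats this and says: "Participants are analyzed based on the group to which they are assigned using all available data". In B.2, "Analyses of the treatment effects on PROs will employ the same" t test approach. Mixed models are specified only for the ecological measures (B.2) and for the longitudinal dosing and treatment-progress analyses (B.3.c).

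B.4.a expects 3 to 6 missing-data patterns for neural targets and PROs, proposes an indicator for each, and concludes: "If results are not much altered by inclusion of pattern indicators, then concern about missing data assumptions is diminished". B.4 and B.4.a both also say that no test exists for data missing not at random (MNAR).

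**The concern.** The MAR protection described in B.4 belongs to a model that is not the one specified for the go/no-go estimate. A t test on change needs both visits, so using all available data does not bring in a participant whose week-16 scan is missing. Criterion 1 is read against a point threshold, d of at least 0.3, so a shift in the estimate from dropout counts directly.

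The arms need not drop out alike. B.4 itself describes people leaving because treatment has or has not worked, and waitlist participants have no access to Lumen until after their week-16 assessment (section 7.0).

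The B.4.a sentence could then lead the team to set aside outcome-related dropout on the strength of a check that cannot see it for the neural targets.

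**Working it through.** **Inputs from the documents.** Allocation is 40 Lumen and 20 waitlist. At 85% retention, 0.85 × 40 = 34 and 0.85 × 20 = 17 remain, so 6 and 3 are missing. The threshold is d = 0.3, which B.1 sets at half of the earlier trial's 0.6 (0.5 × 0.6 = 0.3). Neural targets are measured at weeks 0 and 16 only (B.1) and scored so that higher is better. Baseline measures are completed before randomisation (section 5.0), so the missing value is the week-16 one.

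**Assumed.** Unit-variance normal outcomes, true effect 0, and week 0/16 correlation ρ = 0.3 or 0.5. The documents give no value for ρ. Paired results below are for ρ = 0.3 / 0.5. Waitlist dropout is random unless stated.

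**1. Reference case, random dropout.** The standard error of d is √(1/34 + 1/17) = 0.297. The chance of d ≥ 0.3 on one target with no true effect is P(t with 49 df > 0.3/0.297 = 1.01) = 0.16.

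**2. The t test when only Lumen dropout depends on baseline.** Suppose the six best Lumen baselines are lost. The expected mean of the top six of 40 standard normal values is 1.51, so the remaining 34 have a mean baseline of −6 × 1.51/34 = −0.266. Their expected change is (1 − ρ) × 0.266, which is 0.19 / 0.13 raw SD. Dividing by the SD of change, √(2(1 − ρ)) = 1.18 / 1.00, gives 0.16 / 0.13 in units of d.

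**3. Simulation, 20,000 trials per cell (Monte Carlo SE 0.002).** The baseline-adjusted estimate is the ANCOVA coefficient. It equals the likelihood estimate with a common baseline mean, because only week 16 is missing. Biases are in raw SD.

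| Dropout | t test | Baseline-adjusted | P(d ≥ 0.3), t test |
|---|---|---|---|
| Best baselines lost in both arms | 0.005 / 0.004 | 0.000 / 0.001 | 0.172 / 0.169 |
| Best six Lumen baselines lost | 0.188 / 0.133 | 0.000 / −0.001 | 0.335 / 0.298 |
| Softer baseline dependence, Lumen only | 0.101 / 0.073 | 0.002 / 0.001 | 0.239 / 0.226 |
| Worst six Lumen week-16 values lost | 0.186 / 0.134 | 0.247 / 0.211 | 0.330 / 0.299 |
| Six least improved Lumen lost | 0.315 / 0.268 | 0.221 / 0.212 | 0.504 / 0.508 |
| Lumen non-improvers leave, symptom change correlated 0.4 (assumed) with neural change | 0.125 / 0.108 | 0.083 / 0.083 | 0.260 / 0.267 |
| Lumen improvers leave, same correlation | −0.127 / −0.105 | −0.082 / −0.080 | 0.086 / 0.089 |

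The bias can also run against Lumen under baseline-dependent dropout. In a separate large-sample run with true d 0.15, ρ = 0.5 and low Lumen baselines more likely to be lost, the t test gave 0.06 and the mixed model 0.15.

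**4. What the pattern indicator can show.** In the t test, everyone with a change score is a completer, so the indicator is constant and cannot alter the result. In a mixed model with intercept, group, time, group × time, pattern and pattern × time, the observable cells are completers at two visits in each arm (4) and dropouts at week 0 in each arm (2). Pattern × time is zero in all six cells, so six columns have rank 5. The term that would carry the dropouts' different change is not estimable. In the same large-sample run (true d 0.15), outcome-related Lumen dropout moved the mixed-model estimate to 0.299, and the estimate with the indicator was also 0.299.

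**The case against.** **Criterion 1 is explicitly tied to the t test where it is defined.** B.4 is general text, so the conflict may be a wording slip. That is the natural reading, and the documents do not support calling these two rival decision rules. What stands is that B.4's justification does not apply to the t test.

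**B.2 does not call mixed models primary.** Its sentence "In all analyses, all available data for each DV will be used and missing data will be handled directly through maximum-likelihood estimation" closes the paragraph on ecological measures and may cover only those. It is supporting text here and no more.

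**The plan has other safeguards.** It commits to MAR imputation, to varying the imputation models, and to examining missingness by condition and covariate subgroup. A reader might infer that dropout is ignored, and that would be wrong. Yet none of these steps identifies the missing week-16 values. The mice simulation and the SCALE option are mentioned without commitment.

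**The indicator can move a mixed-model estimate.** This happens when dropout fractions differ between arms. With 8 Lumen and 1 waitlist missing, the average move was 0.155 / 0.110 when the best baselines were lost and 0.051 / 0.056 when the worst week-16 values were lost. So it cannot be said that the indicator never changes anything. Most of the outcome-related bias remained, and the identification argument is unaffected. Patterns defined across outcomes, such as survey done and scan missed, can inform an observed PRO but not the missing scan.

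**The sizes depend on the scenario.** This is true. Missing sessions is not the same as missing the week-16 visit, which carries an incentive, and symptom-driven bias of about 0.1 SD is small beside the planned half-width of 0.5.

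**Conclusion.** Both points hold and should be corrected. First, the MAR property claimed in B.4 does not attach to the estimate read against d = 0.3. If dropout depends on baseline in the Lumen arm only, the t test is biased by up to about 0.19 / 0.13 raw SD in the extreme case and 0.10 / 0.07 in a softer one. If that dependence is alike in both arms, it is unbiased. Second, for outcomes with two waves, an unchanged result after adding pattern indicators is no evidence against outcome-related dropout, and saying otherwise conflicts with the plan's own statement that MNAR cannot be tested. The second point needs no simulation.

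The sizes rest on the assumed correlations, 15% missing in each arm and the chosen dropout mechanisms. They are illustrations, not forecasts. A reader might take the probabilities as the chance of a wrong move to the next phase. They are not: they concern Criterion 1 on one target, and Criterion 2 and the feasibility and acceptability milestones must also be met. Nor do the results show that a mixed model would resolve outcome-related dropout.

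**What to change.** **(a) Name one primary analysis for Criterion 1 and the PROs**, in the same words in 9.0, B.1, B.2 and B.4. The preferred choice is a baseline-adjusted week 0/16 likelihood model including all randomised participants, with the SD that standardises d stated. The SD matters: at ρ = 0.3, d = 0.3 is 0.3 × 1.18 = 0.35 raw SD on the SD of change, but 0.30 on the SD at a single visit. The downsides should be written down:

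- It is a change of estimator. Even with complete data it differs from the t test by a mean absolute 0.15 / 0.11 SD per trial.
- It protects only when missingness depends on variables in the model.
- Under MNAR it may be more or less biased than the t test (table above).

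If the t test is kept, remove the MAR claim for it and designate the imputed analysis as the MAR check.

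**(b) For two-wave outcomes, delete the sentence saying that concern is diminished.** Commit to a delta-adjusted analysis within the planned PROC MI run: shift the imputed week-16 values over a grid, separately by arm, and report the shift at which d falls below 0.3. Recompute d, including its SD, from the shifted data. For scale, with 6 of 40 Lumen values imputed, a 1 SD shift moves the Lumen mean by 6/40 = 0.15 SD.

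The cost is SAP text, a decision on the estimator and one short analysis. Data collection and sample size do not change.

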## Appendix 4. Study Event Windows

### Event windows (in Days)

Preferred windows (in Days)	ES	V1	EMA#1	R														V2		
Lumen PST:					Orient.	S1	S2	S3	S4		S5		S6		S7		S8			
Week (indexed from randomization) #: from	-4	-2		0	1	1	2	3	4		6		8		10		12		14	
to	-2	-1			2	3	4	5	6		8		10		12		14		18	
IES-eligible to eConsent, max. days	14			Randomization																
eConsent to V1, max. days		14																		
IES-eligible to V1 (rescreen if IES-V1>90d), max. days		28																		
V1 to EMA#1 start (automated), max. days		1																		
V1 to Randomization, max. days			10																	
Randomization to Lumen Orientation Visit, max. days						14														
Lumen Orientation to Session 1, max. days							7													
Lumen Session to Session, max. days								7	7	7		14		14		14		14		
Randomization to V2, target 112d (16 weeks) +/- allowable 14d window (14-18 weeks)																				112 +/-14

Abbreviations: IES, initial eligibility screening; EMA, ecological daily assessment; PST, problem solving treatment; S1-S8, sessions 1-8 with Lumen; V1, visit 1; V2, visit 2

